5.7 Blinding and Procedures for Unblinding the Study

This is an open-label study, and there are no procedures for blinding and unblinding.

5.8 Management of AFM24-Related Toxicities

Any DLT during Cycle 1 in the Phase 1 part: Permanently discontinue AFM24.

Please see APPENDIX F (Section 14.6) for a summary of management of IRR/CRS, and other AFM24-related AEs.

Fever: Subjects who develop fever during AFM24 treatment should be supported with antipyretic medications such as paracetamol or metamizole-sodium. If the subject develops high fever (above 40°C body temperature) physical cooling of the body, e.g., with cold packs should be considered. AFM24 treatment is recommended to be held for subjects who have body temperature $\geq 38^\circ\text{C}$ until temperature normalizes below 38°C.

Cytokine release syndrome: See APPENDIX F (Section 14.6; grading and management of IRRs, CRS, and other AFM24-related AE) for detailed grading criteria and detailed guidance on management.

Dermatological toxicities: Investigators are asked to pay special attention to ALL dermatological toxicities and consult with a dermatologist if needed. In cases of \geq Grade 3 skin toxicity, AFM24 treatment should be interrupted or postponed until the reaction resolves to \leq Grade 1 or baseline. Subjects should be asked to limit direct sunlight exposure and apply protective sun cream during treatment with AFM24. A rechallenge should be considered at the discretion of the Investigator but AFM24 should be permanently discontinued with a recurrence of Grade 3 skin toxicity.

IRRs: See APPENDIX F (Section 14.6; grading and management of IRs, CRS, and other AFM24-related AEs) for detailed grading criteria and detailed guidance on management.

Electrolyte abnormalities: Consider withholding AFM24 for \geq Grade 2 electrolyte abnormalities and resume when resolved. Replenish electrolytes as medically appropriate.

Pulmonary symptoms: In the event of acute onset or worsening of pulmonary symptoms, interrupt AFM24 therapy. Discontinue AFM24 therapy if interstitial lung disease is confirmed.

Hepatotoxicity: If severe (CTCAE Grade ≥ 3) hepatic impairment develops for subject with/without liver metastasis, AFM24 should be discontinued permanently.

Gastrointestinal Perforation: Permanently discontinue AFM24 in subjects who develop gastrointestinal perforation.

Other: For all CTCAE Grade 3 toxicities other than those that meet the definition of a DLT during Cycle 1 of the dose escalation (i.e., Phase 1) phase, and other than those described above, interrupt treatment with AFM24 until resolved to Grade ≤ 1 or baseline. If CTCAE Grade 3 toxicity recurs upon rechallenge or in case of CTCAE Grade 4 toxicity, permanently discontinue treatment.

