In Scenario 2 (high-toxicity scenario), the starting dose has already 20% probability of observing at least 1 DLTs in the first cohort if 2 subjects enrolled. This contributes to the high percentage 22.6% of all simulated studies for which the study is stopped since none of the doses is considered tolerable anymore. This is an expected situation for a high-toxicity scenario.

In Scenario 3, 33.8% of the simulated studies declared a dose as MTD with true DLT rate in the targeted dose range.

The mean subject numbers range from 13.9 subjects (high scenario) to 18.57 subjects (true dose toxicity scenario) and the maximum number of subjects was 43. The low mean number of subjects in the high toxicity- scenario is explained by the frequent stopping of the study.

In summary, the considered data scenarios show a reasonable behavior of the model and the operating characteristics demonstrate a good precision of MTD determination.

14.6 APPENDIX F: Grading and Management of Infusion-related Reactions, including Anaphylaxis, Allergic Reaction, and Cytokine Release Syndrome

Investigators are asked to pay special attention to IRRs, which include hypersensitivity reactions and CRS. These reactions may be experienced by subjects during the infusion of investigational treatment (uniphasic reaction) and/or within hours of an infusion (biphasic/delayed reaction). The reaction may be caused by the therapeutic agent, diluent, or delivery vehicle. IRRs can have a broad variety of symptoms; from mild to moderate chills, flushing, itching, skin rashes, heart rate/blood pressure alterations, dyspnea, chest discomfort, back/abdominal pain, nausea, vomiting, diarrhea to severe and life threatening anaphylactic/anaphylactoid reactions; mostly appearing during or immediately after the investigational drug infusion. Special attention must be paid to CRS during investigational treatment which can manifest with fever, cardiac dysfunction, acute respiratory distress syndrome, neurologic toxicity, renal and/or hepatic failure, and disseminated intravascular coagulation. Skin rash, as well as gastrointestinal symptoms of nausea, vomiting or diarrhea may also occur. Fever is a hallmark for CRS, and many features of CRS can also mimic infection.

The aim of this appendix is to:

Provide guidance on monitoring for IRR/CRS

Provide guidance on the grading of IRR/CRS

Provide guidance on management of IRR/CRS.

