14.6.2 Grading and Reporting of IRR/CRS

Any treatment-related IRRs are defined according to the NCI CTCAE v5.0 definition (Injury, poisoning and procedural complications). Symptoms occurring during or following infusion of investigational treatment may also be defined according to AE categories such as allergic reaction,

anaphylaxis, or cytokine release syndrome. If an allergic reaction, anaphylaxis or cytokine release syndrome is related to the infusion of AFM24, the term “infusion-related reaction” should be reported. In addition, Investigators are encouraged to use any additional terms to further describe the event (e.g., anaphylaxis, cytokine release syndrome, hypotension, bronchospasm, hypoxia).

The National Cancer Institute’s Common Terminology Criteria for Adverse Events ([CTCAE v5.0](#)) contains a grading system for IRR and related events as provided in [Table 22](#).

Table 22: Grading System for IRR and Related Events According to CTCAE v5.0

CTCAE Term	Grade 1	Grade 2	Grade 3	Grade 4	Grade 5
Infusion related reaction	Mild transient reaction; infusion interruption not indicated; intervention not indicated	Therapy or infusion interruption indicated but responds promptly to symptomatic treatment (e.g., antihistamines, NSAIDs, narcotics, i.v. fluids); prophylactic medications indicated for ≤ 24 hours	Prolonged (e.g., not rapidly responsive to symptomatic medication and/or brief interruption of infusion); recurrence of symptoms following initial improvement; hospitalization indicated for clinical sequelae	Life-threatening consequences; urgent intervention indicated	Death
Definition: A disorder characterized by an adverse reaction to the infusion of pharmacological or biological substances					
Navigational Note: Not applicable					
Allergic reaction	Systemic intervention not indicated	Oral intervention indicated	Bronchospasm; hospitalization indicated for clinical sequelae; intravenous intervention indicated	Life-threatening consequences; urgent intervention indicated	Death
Definition: A disorder characterized by an adverse local or general response from exposure to allergen.					
Navigational Note: If related to infusion, use Injury, poisoning, and procedural complication: Infusion related reaction. Do not report both					
Anaphylaxis	-	-	Symptomatic bronchospasm, with or without urticaria; parenteral intervention indicated; allergy related edema/angioedema; hypotension	Life-threatening consequences; urgent interventions indicated	Death

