Definition: A disorder characterized by an acute inflammatory reaction resulting from the release of histamine and histamine-like substances from mast cells, causing a hypersensitivity immune response. Clinically, it presents with breathing difficulty, dizziness, hypotension, cyanosis and loss of consciousness, and may lead to death.					
Navigational Note: Not applicable.					
Cytokine release syndrome	Fever with or without constitutional symptoms	Hypotension responding to fluids; hypoxia responding to $<40\%$ oxygen	Hypotension managed with 1 pressor; hypoxia requiring $\geq 40\%$ oxygen	Life-threatening consequences; urgent interventions indicated	Death
Definition: A disorder characterized by fever, tachypnea, headache, tachycardia, hypotension, rash, and/or hypoxia caused by the release of cytokines.					
Navigational Note: Also consider reporting other organ dysfunctions including neurological toxicities such as: Psychiatric disorders: Hallucinations or Confusions; Nervous system disorders: Seizure, Dysphasia, Tremor, or Headache					

CTCAE = Common Terminology Criteria for Adverse Events; i.v. = intravenous; NSAID = nonsteroidal anti-inflammatory drug.

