14.6.3 IRR/CRS Management

The management of IRR and other related AEs is summarized in [Table 23](#).

Table 23: Summary of Management of Infusion Related Reactions, including Anaphylaxis, Allergic Reactions, and Cytokine Release Syndrome*

CTCAE v5.0 Grade	Action to AFM24	Actions and medication to manage toxicity
Grade 1	Continue treatment without modification	Vigilant supportive care and treat in line with institutional practice including needed workup to rule out other differential diagnoses
Grade 2	
Interrupt treatment and restart when symptoms resolve to \leqCTCAE Grade 1 or baseline
 
Consider infusing the next AFM24 infusion with a >4-hour infusion time
	
Vigilant supportive care and treat in line with institutional practice including needed workup to rule out other differential diagnoses
 
Consider symptomatic medication such as antihistamines, antipyretics, steroids, i.v. fluids, oxygen, as appropriate, and in line with institutional practice
 
In case subject of older age and/or with extensive co-morbidities and CRS, consider: Administer tocilizumab 8 mg/kg (maximum 800 mg) i.v. over 60 min; may administer up to 3 additional doses of tocilizumab 8 mg/kg (maximum 800 mg) if no clinical improvement in signs/symptoms of CRS after first dose. Start corticosteroid treatment (e.g., methylprednisolone 2mg/kg/day)

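### For an infusion-associated fever of 38°C or above with no Grade 2 feature, Section 5.8 recommends a hold while Table 23 can say continue, and Section 14.6.2 does not say which Table 22 row sets the grade

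*Protocol*

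**What the plan says.** Section 5.8 of the protocol, on managing AFM24-related toxicities, has separate paragraphs for fever, CRS and IRRs. The fever paragraph opens: "Subjects who develop fever during AFM24 treatment should be supported with antipyretic medications". It goes on: "AFM24 treatment is recommended to be held for subjects who have body temperature" of 38°C or above, "until temperature normalizes below 38°C". The CRS and IRR paragraphs only send the reader to Appendix F for grading and management.

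The introduction to Appendix F (Section 14.6) notes: "Fever is a hallmark for CRS". Table 22 in Section 14.6.2 describes Grade 1 CRS as "Fever with or without constitutional symptoms", with no temperature threshold. Table 23 in Section 14.6.3, whose title covers both IRR and CRS, gives the action on AFM24 at Grade 1 as "Continue treatment without modification".

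On reporting, Section 14.6.2 says: "If an allergic reaction, anaphylaxis or cytokine release syndrome is related to the infusion of AFM24, the term" to be used is infusion-related reaction. On the IRR row of Table 22, Grade 1 is a mild, passing reaction that calls for neither interruption nor intervention. Grade 2 begins "Therapy or infusion interruption indicated but responds promptly to symptomatic treatment".

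**The concern.** A subject whose temperature reaches 38.4°C during an infusion, with no other sign, falls under the fever paragraph of Section 5.8. If the fever is judged to be CRS, the subject also falls under the Grade 1 row of Table 23. One recommends a hold and the other says to carry on unchanged. The grade may also depend on which row of Table 22 the site uses, and on whether a hold made under Section 5.8 is taken to mean that interruption was indicated.

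Two things are at stake. Subjects with the same event may be handled differently from site to site. And the boundary between Grade 1 and Grade 2, on which several protocol rules turn, may be drawn differently for the same event. The SAP (Sections 7.8.1 and 7.8.2) tabulates treatment-emergent events by severity grade, events leading to interruption, and dose interruptions, so the ambiguity would also reach the reported results.

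**Working it through.** There is no stated figure to reproduce. The check sets the passages side by side for one event: an isolated fever of 38°C or above during an infusion, judged to be infusion-related, with no Grade 2 feature of CRS (on that row, hypotension or hypoxia).

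1. **Section 5.8, fever paragraph.** Give antipyretics. A hold is recommended until the temperature is below 38°C.
2. **Table 22, CRS row, then Table 23.** Fever alone is Grade 1. Table 23 says to continue without modification, with supportive care and a work-up for other causes.
3. **Table 22, IRR row, then Table 23.** If the antipyretic counts as an intervention, or the hold counts as an indicated interruption, the Grade 1 wording no longer fits and Grade 2 does. Table 23 then says to interrupt and to restart at Grade 1 or lower, or at baseline.

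Paths 1 and 2 give opposite actions. Paths 1 and 3 broadly agree on interruption. Paths 2 and 3 give different grades. So the conflict in action arises only when the CRS row sets the grade, and the documents do not say whether it does: Section 14.6.2 settles the reporting term and stops there.

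The difference between Grade 1 and Grade 2 feeds these rules:

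- Section 5.2: a shorter infusion from the third dose is allowed if the first two produced no IRR/CRS above Grade 1.
- Section 5.3: the same cut-off applies to premedication taper and to shortening post-dose observation from 4 to 2 hours.
- Section 7.2.4, Table 5: the same cut-off decides between the full and the reduced vital-sign schedule.
- Section 5.5: in Phase 1, a drug-related toxicity of Grade 2 or higher rules out intra-subject dose escalation.
- Section 3.5: Cycle 1 toxicity of Grade 2 or higher is one of the inputs to dose decisions.

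**Size.** Section 1.6 reports IRRs in 69% of 29 Phase 1 subjects at the October 2021 cut-off: 0.69 × 29 = 20.01, about 20 subjects. The number of those caught by the conflict is 20 × f × g, where f is the share with a fever of 38°C or above and g is the share of those whose reaction had no Grade 2 feature. Neither f nor g is given. With each free between 0 and 1, the product can be anything from 0 to 20, so no useful count follows.

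**The case against.** The best defence is that Section 5.8 separates the three entities. Fever has its own rule, while CRS and IRR go to Appendix F, so the appendix would naturally govern once a fever is judged to be CRS or IRR. Appendix F supports that reading by asking for a work-up of other causes even at Grade 1 and by noting that CRS can resemble infection. This is sensible, but it has to be inferred: the fever paragraph makes no exception for CRS or IRR, sits under AFM24-related toxicities, and states no order of precedence.

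Four further points narrow the finding, and they stand.

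- A reader might infer two mandatory and opposite orders. The text does not support that. Section 5.8 only recommends a hold, and the sentence can be read as covering a febrile subject about to be dosed, although it does not say so.
- A reader might infer that the two sections always conflict. They do not. On the IRR row, a fever needing antipyretics or interruption fits Grade 2, which Table 23 also interrupts. Fever from another cause falls only under Section 5.8.
- A reader might put a count on it, for instance 5 to 10 of 29 by supposing that a quarter to a half of the 20 IRR subjects were febrile. That share is not in the documents, and the count ignores that only reactions graded 1 overall lead to the instruction to continue. Nor do the documents call infusion fever the expected reaction of this drug class. Section 8.3.1 places IRRs within the anticipated safety profile and lists fever as one manifestation among many.
- A reader might infer that the dose-escalation model is affected. Section 3.4.2 feeds only Cycle 1 dose-limiting toxicities into it, so a Grade 1 versus Grade 2 difference does not enter. Shorter infusions, shorter observation and tapering are also optional.

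Finally, Cohorts A and C were stopped for futility and Cohort B enrolment ended at 8, so few subjects would be affected from now on. Section 3.9 does keep subjects still receiving study drug on treatment, and the grades already collected still have to be reported.

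**Conclusion.** The point holds in a limited form. For an infusion-associated fever of 38°C or above with no Grade 2 feature, the Section 5.8 recommendation to hold conflicts with the Table 23 Grade 1 instruction to continue whenever the CRS row sets the grade, and no passage says which governs. Separately, because Section 14.6.2 does not name the grading row, the same fever can be Grade 1 or Grade 2, on either side of cut-offs that the protocol uses for infusion time, premedication, observation, vital signs and intra-subject escalation. The grade difference is conditional: it needs the site to treat the antipyretic or the hold as an intervention or interruption that was indicated. The number of subjects affected is unknown. This is an inconsistency in wording with consequences for safety handling and for IRR grading. It should be corrected, but it does not bear on the primary analyses.

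**What to change.** Reconcile the fever paragraph of Section 5.8 with the Grade 1 row of Table 23, and have each refer to the other, so that a single instruction applies to fever judged to be IRR or CRS. In Section 14.6.2, state which row of Table 22 grades such a fever, and whether a hold made only because of the temperature rule counts as an indicated interruption. Which clinical instruction to keep is for the sponsor to decide.

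The cost is a wording change in Section 5.8 and Appendix F and a memo to sites. It needs no extra procedures.

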6.0 STUDY DRUG MATERIALS AND MANAGEMENT

6.1 Provision and Replacement of AFM24

Sufficient doses of AFM24 study drug will be supplied. Where study drug supplies (or packaging) are apparently damaged on receipt or considered unfit for use by the study site, the Sponsor (or their delegate) must be notified immediately. Where required, clinical study supplies will be replaced. Further details on the handling of AFM24 study drug at site will be described in the Pharmacy Manual.

6.2 Labeling of AFM24

AFM24 clinical study supplies will be labeled in compliance with Good Manufacturing Practice Annex 13 requirements, United States (US) FDA requirements, and any other applicable local regulatory guidelines.

6.3 Storage of AFM24

AFM24 study drug will be shipped to the site and must be stored at the site in a secure location under controlled conditions and in the required temperature range. Please see the Pharmacy Manual for further details.

6.4 Drug Accountability

The Investigator is obliged to keep sufficient documentation of the delivery, use, and destruction or return of unused, used, or partially used AFM24 study drug. The documentation must include dates, quantities, subject numbers, batch numbers, or other identification number. The Investigator may assign some or all the Investigator's duties for drug accountability to an appropriate pharmacist. Roles and responsibilities of site staff will be recorded in the Investigator Site File.

The Investigator should maintain records that document adequately that the subjects were administered the doses specified in the protocol and reconcile all AFM24 study drug received for the study. The local clinical research associate (CRA) will be responsible for checking the drug accountability records maintained by the site during study monitoring visits.

AFM24 provided for this study is for use only as directed in the protocol. It is the Investigator and their institution's responsibility to establish a system for handling study drug to ensure that:

- Deliveries of AFM24 are correctly received by a responsible person;
- Such deliveries are recorded;
- Study drug is handled and stored safely and properly as stated on the label;
- Study drug is only dispensed to study subjects in accordance with the protocol; and
- Any unused study drug is destroyed locally or returned for destruction in liaison with the CRA after written approval by the Sponsor.

Certificates of delivery and return must be signed by the responsible pharmacist and copies retained in the Pharmacy File. Throughout the study, it must be possible to reconcile delivery records with records of usage and any destroyed/returned stock of AFM24. To help with compliance checks, records of usage should include an appropriate form of identification of the subject to whom the study drug was dispensed (using an indirect form to allow cross reference to the subjects' identity), plus the quantity and date of dispensing.

The return or destruction of unused drug will be conducted after written approval by the Sponsor, with appropriate documentation and drug accountability procedures completed following destruction.

7.0 STUDY PROCEDURES

The schedule of assessments to be followed for weekly and q2w dosing regimens are provided in APPENDIX A [[Table 11](#) through [Table 15](#)] and APPENDIX B [[Table 16](#) through [Table 18](#)], respectively.

Safety will be assessed by periodic vital signs, physical examinations, ECOG PS, 12-lead ECGs, clinical laboratory assessments, and monitoring of AEs. AEs will be graded using the NCI CTCAE, v5.0 ([NCI 2017](#)).

All AEs and SAEs that are related to study procedures occurring during pre-screening as well as all AEs and SAEs occurring from the time the subject signs the main ICF up to and including the Safety Follow-up visit (30 days [± 5 days] after the last administration of AFM24) or until the start of a new anti-cancer treatment, whichever is sooner, will be collected. Adverse events occurring after signing of the Main ICF but prior to the first dose of study drug shall be recorded on the Medical History eCRF page (**Note:** any SAEs which are related to study procedures and occur during pre-screening and any SAEs that occur after the subject signs the Main ICF and prior to the first dose of study drug will still be reported using the SAE form).

7.1 Volume of Blood Sampling

Total blood volumes required during study participation will be provided in the ICF provided to each subject. Efforts will be made to limit blood sampling to avoid any redundancy. The requirements for blood sampling will be described and maintained in the Lab Manual.

7.2 Description of Study Interventions and Assessments

Details of the procedures to be followed for specified study assessments for weekly and q2w dosing regimens are provided in APPENDIX A (Section [14.1](#)) and APPENDIX B

(Section 14.2), respectively. During the study, additional assessments may be carried out as clinically indicated.

7.2.1 Informed Consent, Medical History, and Demographics

Before starting the pre-screening process (for subjects in Phase 2a) or screening process, written informed consent will be obtained. Demographic information will be collected during the Screening visit. There will be a baseline assessment of relevant medical history and cancer history conducted at Screening to confirm eligibility and to record significant medical history and concurrent illnesses. Concurrent illnesses recorded at Screening (excluding the primary disease under evaluation) that worsen in severity or frequency from this baseline assessment during the study should be reported as AEs (see Section 8.1).

